Evaluable:	Meeting all eligibility criteria, and, therefore, included in the analysis (see Section 5.3 for details on criteria for evaluability).
Key coded information:	Refers to encoded or otherwise pseudoanonymised PII from which direct identifiers have been removed and replace by a unique identifier or random code. Key coded

PII shall not be considered anonymised information.

**Non-interventional
(observational) Human
Subject Research:**

Studies where medicinal products, should they be administered, are prescribed in normal (routine) medical practice. No medical care or medical/scientific procedures as required in a research protocol are administered to participants except as part of routine medical care.

**Personally Identifiable
Information:**

Refers to information, regardless of the medium in which such information is held or expressed, that identifies or that reasonably could be used to identify an individual.

Retrospective study:

A study that looks backward in time (e.g. at events that occurred in the past; outcomes and exposure can no longer be influenced), usually using medical records, databases or interviews in order to address one or more study endpoints.

Self-contained study:

Study with objectives not linked to the data of another study.

Study population:

Sample of population of interest.

Subject:

Term used throughout the protocol to denote a person about whom some medical information has been recorded in a database.

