#### **5.1.2. Total cohort**

The Total cohort will comprise of all eligible subjects included in the study.

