### **5.2. Criteria for eliminating data from Analysis Sets**

Not applicable for database studies

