## 6.2. Primary objective

### 6.2.1. Analysis of primary objective planned in the protocol

The proportion of subjects with influenza caused by seasonal influenza A and/or B among all influenza cases reported with exact 95% confidence interval (CI) by age, A-virus subtype and B-strain lineage and overall will be calculated.

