## 9. CHANGES FROM PLANNED ANALYSES

- There will be an interim analysis planned on available data (lab database for Panama) in order to submit the abstract\poster for SLIPE congress
- We will also be reporting the number of specimen samples received per year within the ICGES influenza surveillance system for influenza testing at aggregated level (considered as screened cohort) and determine the proportion that tested positive for Influenza to describe the reporting capabilities of the surveillance system at capturing influenza A and B cases.
- We will also be including seasonal 2016 data as it is presently available. Based on the dates of data transfer, the end time period may be expanded if data is available during data transfer
- All the statistical analysis will be performed on specimens instead of subjects because a subject can provide more than one influenza positive specimens.
- The age group used for the analysis are 0-4, 5-17, 18-49, 50-64 and >=65 years instead of <1, 1-4, 5-9, 10-14, 15-19, 20-24, 25-44, 45-49, 50-59, 60-64 and ≥ 65 years.

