## 10. LIST OF FINAL REPORT TABLES, LISTINGS AND FIGURES

The TFL TOC provides the list of tables/listings and figures needed for the study report. It also identifies the tables eligible for each analyses and their role (synopsis, in-text, post-text, SHS, CTRS). Note that all TFL aimed to be included as post-text are noted as post-text even if these are tabulation of individual data such as listing of SAE. The post-text material contains all source material for the study report and accordingly a post-text table may be redundant with an in-text table.

The mock tables referred under column named 'layout' can be found in **PPD** **PPD** dedicated folder for standard tables and in Annex 3 for study specific mock table/figure/listing. The latter table/figure/listing are identified by the prefix SS\_ in the TFL Toc.

The following group names will be used in the TFLs:

Group order in tables	Group label in tables	Group definition for footnote
P	Influenza A	Positive for Influenza A
P	Influenza B	Positive for Influenza B
Or/and		
P	H1N1	Positive for Influenza A subtype H1N1
P	H3N2	Positive for Influenza A subtype H3N2
Or/and		
P	Victoria	Positive for Influenza B lineage Victoria
P	Yamagata	Positive for Influenza B lineage Yamagata
Or/and		
P	0-4	0-4 years of age
P	5-17	5-17 years of age
P	18-49	18-49 years of age
P	50-64	50-64 years of age
P	>=65	>=65 years of age
Or/and		
P	West	West: Boca del Toro, Chiriquí and Comarca Nobe Bugle
P	Central	Central: Coclé, Herrera, Los Santos and Veraguas
P	Panama	Panamá: Panamá Este, Panamá Oeste, Panamá Metro and San Miguelito
P	Northeast	Northeast: Colón, Darién and Kuna Yala

Influenza season		
Calendar year (Jan-Dec)	Southern Hemisphere (May-Oct)	Northern Hemisphere (Oct-May)
Jan-Dec 2010	May– Oct 2010	Oct 2010-May 2011
Jan-Dec 2011	May– Oct 2011	Oct 2011-May 2012
Jan-Dec 2012	May– Oct 2012	Oct 2012-May 2013
Jan-Dec 2013	May– Oct 2013	Oct 2013-May 2014
Jan-Dec 2014	May– Oct 2014	Oct 2014-May 2015
Jan-Dec 2015	May– Oct 2015	Oct 2015-May 2016
Jan-Dec 2016	May– Oct 2016	Oct 2016-May 2017

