## 11. ANNEX 1 STANDARD DATA DERIVATION RULE AND STATISTICAL METHODS

### 11.1. Statistical Method References

- The exact two-sided 95% CIs for a proportion within a group will be the Clopper-Pearson exact CI [Clopper CJ, Pearson ES. The use of confidence or fiducial limits illustrated in the case of binomial. *Biometrika*. 1934;26:404-413].
- WHO recommendations on the composition of influenza virus vaccines by influenza season can be found under:  
<http://www.who.int/influenza/vaccines/virus/recommendations/en/>

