**11.2.3. Case definition**

- Influenza is defined as any positive laboratory test from one or more of the clinical specimens [Guidelines for the epidemiological surveillance of influenza, 2012].

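### Counting positive specimens rather than subjects lets repeat positives from one illness enter the Total cohort tables as separate cases, with no rule for them and no count of them

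*SAP*

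**What the plan says.** SAP section 9 declares the change and its reason: "All the statistical analysis will be performed on specimens instead of subjects because a subject can provide more than one influenza positive specimens". The footnotes of the Total cohort templates follow it. N is the number of influenza-positive specimens in Template 3 (demographics and patient type), Templates 17-18 (type by year and season) and Templates 30-31 (outcome). Several titles, such as those of Templates 5 and 17, nevertheless speak of cases.

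Other parts of the plan still use the person or the illness as the unit:

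- SAP 5.1.2: "The Total cohort will comprise of all eligible subjects included in the study". The protocol glossary defines a subject thus: "Term used throughout the protocol to denote a person about whom some medical information has been recorded in a database".
- SAP 11.2.3: "Influenza is defined as any positive laboratory test from one or more of the clinical specimens". Several positive specimens can therefore support one case.
- Template 24 (signs and symptoms) gives N in specimens, but its percentage footnote divides by subjects.

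No text removes, links or counts repeats. SAP 5.2 on eliminating data reads "Not applicable for database studies". SAP 6.2.2 adds nothing to the primary analysis, and Annex 2 on elimination codes is marked not applicable. Annex 1 covers dates, age, missing data, the case definition, decimals and the interval method.

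**The concern.** The SAP gives repeat positives as its reason for changing every analysis, and then does not say what to do with them. Each positive becomes a record, including second and third positives from the same illness.

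For laboratory throughput (the Screened cohort, Templates 1-2) that is the right unit. It is the wrong unit for facts about a person or an illness: age, sex, patient type, comorbidity, symptoms and outcome. A patient who died and had two positive specimens would appear as two deaths. The protocol rationale wants data on hospitalisation and mortality, and data fit for health-economic models, so others may reuse these counts.

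A second, smaller effect concerns the exact intervals in Templates 11-22. They treat each specimen as independent, and repeats from one illness are not.

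Positives from separate illnesses in the same person are properly separate and are not at issue.

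**Working it through.** **Inputs.** Protocol Table 2 (Panama, 2010-2014) gives influenza positives of 207, 47, 276, 190 and 140, and influenza B positives of 14, 0, 178, 0 and 55. The smallest and largest yearly totals, 47 and 276, reproduce the range stated in protocol 5.2. The sums are 207+47+276+190+140 = 860 and 14+0+178+0+55 = 247. The interval method is in SAP 11.1: "The exact two-sided 95% CIs for a proportion within a group will be the Clopper-Pearson exact CI". The repeat rate is not in the documents, so I assume that a fraction f of subjects have exactly two positives of the same type from one illness, with f = 2, 5, 10 or 20%.

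**1. Case counts.** Specimens = cases × (1+f), so cases = 860/(1+f). This gives 843, 819, 782 and 717.

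**2. Hospitalised share (Templates 3-4).** Let h be the true share; 20% and 50% are assumed for illustration.

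- *All repeats fall in hospitalised cases, with f a fraction of all subjects.* Tabulated share = (h+f)/(1+f). For h = 20% and f = 10%: 0.30/1.10 = 27.3%.
- *Only a fraction f of hospitalised cases have a repeat.* Tabulated share = h(1+f)/(1+hf). For h = 20% and f = 10%: 0.22/1.02 = 21.6%.
- *Repeats are spread evenly.* Numerator and denominator grow by the same factor, and the share stays at h.

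| f | h=20%, f of all subjects | h=20%, f of hospitalised | h=50%, f of all subjects | h=50%, f of hospitalised |
|---|---|---|---|---|
| 2% | 21.6 | 20.3 | 51.0 | 50.5 |
| 5% | 23.8 | 20.8 | 52.4 | 51.2 |
| 10% | 27.3 | 21.6 | 54.5 | 52.4 |
| 20% | 33.3 | 23.1 | 58.3 | 54.5 |

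The 33.3% entry is the extreme: with h = f = 20%, every hospitalised case has a repeat.

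**3. Interval coverage.** Take S specimens made of D concordant pairs and S−2D singles. The count of B positives is X = 2·Bin(D,p) + Bin(S−2D,p). I summed its exact distribution over all values of X whose Clopper-Pearson interval on S contains p. D is S − S/(1+f), rounded.

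| | no repeats | 2% | 5% | 10% | 20% |
|---|---|---|---|---|---|
| 2014, p=55/140 | 95.4 | 94.9 | 94.3 | 93.3 | 91.6 |
| 2012, p=178/276 | 95.6 | 95.2 | 94.6 | 93.6 | 91.8 |
| 2010-2014, p=247/860 | 95.4 | 95.0 | 94.4 | 93.4 | 91.6 |

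For 2014, D = 0, 3, 7, 13 and 23.

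**4. Width after one-record counting.** At the 2014 share of 39.3%, the interval is 16.7 points wide on 140 records. It is 16.9, 17.2, 17.6 and 18.4 points wide on 137, 133, 127 and 117.

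**The case against.** The strongest reply is that the change is open and complete. Section 9 is where departures from the protocol belong, it states one rule (every positive specimen counts), and the template footnotes apply it. The study is descriptive, with no test or decision threshold, and repeats may be rare.

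Much of this stands. A reader might infer that SAP 6.2.1 contradicts section 9, because it still describes "The proportion of subjects with influenza caused by seasonal influenza A and/or B among all influenza cases reported". It does not: that subsection is headed as the analysis planned in the protocol and repeats the protocol text, which section 9 expressly replaces. Nor is this an undisclosed change. The case definition says when influenza is present; it supports counting one illness once but is not itself a counting rule. At 2% repeats the intervals are essentially nominal, and nothing in the documents supports the 10 or 20% scenarios over the lower ones.

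What does not stand is that disclosure settles the matter. Counts and shares are the whole output of a descriptive study, and declaring the unit does not stop one death being counted twice. No Annex 3 template reports how many subjects or repeats lie behind the specimens, so on those templates a reader could not tell a trivial problem from a real one. One limit applies: "The TFL TOC provides the list of tables/listings and figures needed for the study report", and neither that list nor the folder of standard tables was available to check.

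**Conclusion.** The point holds. The rule as written gives wrong counts in the person-level tables wherever one illness yields more than one positive. The cohort definition in 5.1.2 and the Template 24 denominator were not brought into line with it.

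The size is unknown and may be negligible. The figures above rest on an assumed repeat rate, at most two concordant positives per subject, and Panama data for 2010-2014 only. Within that range the clearest effect is on case counts. The effect on shares depends entirely on whether repeat sampling differs by severity, type or age. The loss of coverage is small unless repeats are common.

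A reader might infer that the hospitalised share or the A/B split will be biased. The documents do not support that: they do not say how often repeats occur or in whom. This should be fixed because the remedy is cheap and reporting the number of repeats would settle the question.

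**What to change.** Keep specimen counting for the Screened cohort. For the Total cohort:

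1. Report the numbers of subjects, specimens and repeats by country and year.
2. Add a one-record analysis. Within a subject, positives of the same type and subtype or lineage count once per calendar year, and once per season in season tables. Date the record by earliest onset. If one repeat lacks the subtype or lineage, use the known result.
3. State which value is kept when repeats disagree: for example, the most severe recorded patient type and outcome, and a symptom counted as present if recorded on any repeat.
4. Keep positives of a different type, subtype or lineage as separate records. Flag co-infection only if both come from one specimen or share a complete, non-imputed onset date. SAP 11.2.1 sets missing days to the 15th and missing day and month to 30 June, so imputed dates can coincide by chance.
5. Make the one-record analysis the main one for patient type, outcome, comorbidity and demographics or, at minimum, show it as a sensitivity analysis beside the specimen results.
6. Align 5.1.2, section 9, the table titles and the Template 24 denominator with the chosen unit.

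The cost is SAP wording and one programming step, if specimens can be linked to a person. That is not established. Protocol 1.2 mentions a unique ID and key without saying whether it marks a person or a specimen, 6.5.2 allocates no subject number, and 6.5.4.1 plans identifier checks. If linkage fails, state it as a limitation and label the tables as specimens, not cases.

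The downsides are incomplete matching, merging of a same-strain reinfection within a window, double counting of an illness that crosses a window boundary, record totals that can differ between year and season tables, and slightly wider intervals.

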## 10. LIST OF FINAL REPORT TABLES, LISTINGS AND FIGURES

The TFL TOC provides the list of tables/listings and figures needed for the study report. It also identifies the tables eligible for each analyses and their role (synopsis, in-text, post-text, SHS, CTRS). Note that all TFL aimed to be included as post-text are noted as post-text even if these are tabulation of individual data such as listing of SAE. The post-text material contains all source material for the study report and accordingly a post-text table may be redundant with an in-text table.

The mock tables referred under column named 'layout' can be found in **PPD** **PPD** dedicated folder for standard tables and in Annex 3 for study specific mock table/figure/listing. The latter table/figure/listing are identified by the prefix SS\_ in the TFL Toc.

The following group names will be used in the TFLs:

Group order in tables	Group label in tables	Group definition for footnote
P	Influenza A	Positive for Influenza A
P	Influenza B	Positive for Influenza B
Or/and		
P	H1N1	Positive for Influenza A subtype H1N1
P	H3N2	Positive for Influenza A subtype H3N2
Or/and		
P	Victoria	Positive for Influenza B lineage Victoria
P	Yamagata	Positive for Influenza B lineage Yamagata
Or/and		
P	0-4	0-4 years of age
P	5-17	5-17 years of age
P	18-49	18-49 years of age
P	50-64	50-64 years of age
P	>=65	>=65 years of age
Or/and		
P	West	West: Boca del Toro, Chiriquí and Comarca Nobe Bugle
P	Central	Central: Coclé, Herrera, Los Santos and Veraguas
P	Panama	Panamá: Panamá Este, Panamá Oeste, Panamá Metro and San Miguelito
P	Northeast	Northeast: Colón, Darién and Kuna Yala

Influenza season		
Calendar year (Jan-Dec)	Southern Hemisphere (May-Oct)	Northern Hemisphere (Oct-May)
Jan-Dec 2010	May– Oct 2010	Oct 2010-May 2011
Jan-Dec 2011	May– Oct 2011	Oct 2011-May 2012
Jan-Dec 2012	May– Oct 2012	Oct 2012-May 2013
Jan-Dec 2013	May– Oct 2013	Oct 2013-May 2014
Jan-Dec 2014	May– Oct 2014	Oct 2014-May 2015
Jan-Dec 2015	May– Oct 2015	Oct 2015-May 2016
Jan-Dec 2016	May– Oct 2016	Oct 2016-May 2017

## 11. ANNEX 1 STANDARD DATA DERIVATION RULE AND STATISTICAL METHODS

### 11.1. Statistical Method References

- The exact two-sided 95% CIs for a proportion within a group will be the Clopper-Pearson exact CI [Clopper CJ, Pearson ES. The use of confidence or fiducial limits illustrated in the case of binomial. *Biometrika*. 1934;26:404-413].
- WHO recommendations on the composition of influenza virus vaccines by influenza season can be found under:  
<http://www.who.int/influenza/vaccines/virus/recommendations/en/>

### 11.2. Standard data derivation GSK legacy

#### 11.2.1. Date derivation

- SAS date derived from a character date: In case day is missing, 15 is used. In case day & month are missing, 30June is used.

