6.5.4.1. Check of data set content and format

Prior to starting the programming of the analyses, the GSK person responsible for the analyses will check if the data files content and format meet the requirements for the statistical analyses. This will include (but will not be limited to) checks on the subject/case identifiers consistency, checks on the presence of the analyses variables, checks on list of values and/or codes and checks on the numeric and date formats. Any finding will be feedback to ICGES database owner and require a new transfer, until content and format are appropriate for the statistical analyses.

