6.5.4.2. Check of data completeness and consistency

Any data deficiency such as incomplete data, missing data and data discrepancies that would be detected by GSK statistician or epidemiologist and that are critical for the analyses will be feedback to ICGES database owner. Depending on the possibility of the database owner to correct data, corrected data will be retransferred or not to GSK.

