## **6. STATISTICAL ANALYSES**

Note that standard data derivation rule and stat methods are described in annex 1 and will not be repeated below.

All the analysis on primary and secondary objectives will be performed on Total cohort.

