#### 11.2.2. Demography

- Age at date of onset of the first symptom, will be expressed in years in the study. This will be computed as the difference between the date of onset of the first symptom and the date of birth (only if the data is available).
- The percentages will be computed by using only available information. Only frequencies will be provided for unknown or missing or not applicable categories
- Any measurements omitted or non-evaluable for a particular subject or analysis will not be replaced. Therefore, subjects with omitted or non-evaluable measurements will be excluded from the analysis

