### 13. ANNEX 3: STUDY SPECIFIC MOCK TFL

The following drafted study specific mocks will be used for each country (Panama, El Salvador, Guatemala and Trinidad, Dominican Republic, etc.,)

The data display, title and footnote is for illustration purpose and will be adapted to the study specificity as indicated in the TFL TOC.

Some of these templates were copied from EPI-FLU-032 BOD MX DB (201075) study. Note that there may be few changes between the study specific SAP mock TFL and the final TFLs as editorial/minor changes do not require a SAP amendment

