**Template 4 Summary of demographic characteristics by influenza A subtypes and B lineages - <country> (Total cohort)**

		Influenza A subtypes				Influenza B lineage			
		H1N1 N=XX		H3N2 N=XX		Victoria N=XX		Yamagata N=XX	
Characteristics	Parameters or Categories	Value or n	%	Value or n	%	Value or n	%	Value or n	%
Age [Years]	n		-		-				-
	Mean		-		-				-
	SD		-		-				-
	Median		-		-				-
	Minimum		-		-				-
	Maximum		-		-				-
	Missing		-		-				-
Age group [Years]	0-4								
	5-17								
	18-49								
	50-64								
	>=65								
	Missing		-		-				-
Gender	Female								
	Male								
Region	West								
	Central								
	Panama								
	Northeast								
Patient type	Outpatient								
	Hospitalized								

N = number of influenza positive specimens

n = number of specimen positive in a given category

% = n / Number of specimens with available results x 100

Value = value of the considered parameter

SD = Standard deviation

West: Boca del Toro, Chiriquí and Comarca Nobe Bugle

Central: Coclé, Herrera, Los Santos and Veraguas

Panamá: Panamá Este, Panamá Oeste, Panamá Metro and San Miguelito

Northeast: Colón, Darien and Kuna Yala

**Template 5 Distribution of influenza A cases by month and year - <country>  
(Total cohort)**

Month and year (date of onset of symptoms)	Influenza virus positive (N)	Influenza A positive (n)	Percentage (%)
Jan2010			
Feb2010			
Mar 2010			
Apr2010			
May2010			
Jun2010			
Jul2010			
Aug2010			
Sep2010			
Oct2010			
Nov2010			
Dec2010			
Jan2011			
Feb2011			
....			
Dec2016			

N = number of influenza positive specimens with available test results by month and year

n = number of influenza A positive specimen in a given category

% = (n / N) x 100

**Template 6 Distribution of influenza B cases by month and year - <country>  
(Total cohort)**

Refer to [Template 5](#)

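### The SAP's 30 June rule could count year-only symptom onsets as June cases in the monthly tables, and the SAP does not say whether it or the no-replacement text governs onset month

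*SAP*

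**What the plan says.** SAP 11.2.1 (Date derivation) covers SAS dates derived from text dates: "In case day is missing, 15 is used. In case day & month are missing, 30June is used". It names no variable and exempts none. SAP 6 makes Annex 1, where this rule sits, the standard for the analyses: "Note that standard data derivation rule and stat methods are described in annex 1 and will not be repeated below".

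Templates 5, 7 and 9 in SAP Annex 3 place cases in rows headed "Month and year (date of onset of symptoms", and Templates 6, 8 and 10 refer back to them. The rows run from January 2010 to December 2016, with none for an unknown month. Templates 3 and 4 do have a missing row for age. The denominator is defined as "N = number of influenza positive specimens with available test results by month and year", so it depends on an available test result and not on a recorded onset month.

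SAP 11.2.2 (Demography) says: "Any measurements omitted or non-evaluable for a particular subject or analysis will not be replaced". Its next sentence excludes subjects with such measurements from the analysis. Neither sentence mentions partial dates.

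Protocol 6.5.5 leaves the handling of incomplete data to the SAP and gives partial dates as one example. SAP 11.2.1 is the only rule on partial dates that the SAP contains.

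**The concern.** Mid-year imputation does no harm when a date is needed only to fix the year. In Templates 5-10 the month is the quantity being reported, so the rule would supply the answer instead of leaving it unknown, and nothing in the table would show that it had done so. Temporal distribution is a secondary objective (SAP 3.2), and tabulation by month and year is planned (SAP 6.1.1).

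Two things are at stake. The June counts could include cases whose month was never recorded. And because 11.2.1 and 11.2.2 lead to different treatments, two programmers could obtain different June counts from the same data.

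**Working it through.** **Step 1. What the rule does to each kind of onset date**

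- Day missing, month known: day 15 is used. The month is unchanged for all twelve months, so the monthly tables are not affected.
- Year only: 30 June is used. In each year from 2010 to 2016 this falls in the June row.
- Wholly missing: 11.2.1 gives no value, so the date is not filled.
- Already a numeric date: the rule, as worded, is not triggered.

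Only year-only onsets held as text are at issue.

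**Step 2. The two texts side by side**

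- Under 11.2.1, a year-only onset becomes 30 June and the case enters June in n and N.
- Under 11.2.2, the month is treated as omitted and the case leaves the monthly table.

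The first text is specific to dates. The second is general and sits under Demography. No sentence ranks them.

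**Step 3. Possible size**

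The plan gives no figure to reproduce. Inputs:

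- p, the share of year-only onsets: not in the documents; 1%, 5% and 10% are assumed.
- m, the number of months over which true onsets are evenly spread: assumed 12, or 6 for the May-October season listed in SAP 10.
- Year-only cases are assumed to have the same true month pattern as the others.
- Panama influenza positives, protocol Table 2: 207 + 47 + 276 + 190 + 140 = 860 for 2010-2014.

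True June count = 860/m. Tabulated June = 860(1-p)/m + 860p.

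Ratio of tabulated to true June = (1-p) + mp = 1 + (m-1)p.

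| p | Year-only, of 860 | True June, m=12 | Tabulated June, m=12 | Ratio | True June, m=6 | Tabulated June, m=6 | Ratio |
|---|---|---|---|---|---|---|---|
| 1% | 8.6 | 71.7 | 79.6 | 1.11 | 143.3 | 150.5 | 1.05 |
| 5% | 43.0 | 71.7 | 111.1 | 1.55 | 143.3 | 179.2 | 1.25 |
| 10% | 86.0 | 71.7 | 150.5 | 2.10 | 143.3 | 215.0 | 1.50 |

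Counts are the five Junes of 2010-2014 combined. Cases shown in June that do not belong there = 860p(m-1)/m: 7.9, 39.4 and 78.8 for m=12; 7.2, 35.8 and 71.7 for m=6.

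**Step 4. Season tables**

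The SAP does not say which date assigns a specimen to a season. If it is the onset date, 30 June lies inside the southern season (May-October) and outside the northern one (October-May). Year-only cases would then all count as in season in southern-season countries and all as out of season in northern-season countries.

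**The case against.** The strongest reply is that no problem has been shown. Onset date is a named variable that will be validated before transfer. Protocol 6.5.4.1 checks date formats and requires new transfers "until content and format are appropriate for the statistical analyses". SAS datasets are the preferred format under protocol 6.5.4, and a date that arrives numeric does not trigger the rule. SAP 11.2.2 can be read as dropping a case of unknown month, in which case no June excess arises. The mock tables are not final: "The data display, title and footnote is for illustration purpose and will be adapted to the study specificity". The results are descriptive only.

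Much of this stands. It is why the point is conditional and the size rests on assumption. It does not dispose of the point. A new transfer cannot supply a month that was never recorded, and protocol 6.5.4.2 allows gaps to remain: "Depending on the possibility of the database owner to correct data, corrected data will be retransferred or not to GSK". SAP 11.2.2 does not mention partial dates, so it leaves a conflict and does not settle it. Adding a row to the mocks would capture wholly missing onsets, but year-only onsets would still go to June if 11.2.1 is applied.

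A reader might go further and infer that the June counts will be wrong, or that the lineage and vaccine-mismatch results are biased. The documents support neither. They do not show that any year-only onset exists, and precedence between the two texts is open. Year-only cases would enter both n and N, and nothing indicates that their mix of types or lineages differs from that of other cases.

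**Conclusion.** The point holds as a minor, conditional one. A stated rule, applied as written to a year-only onset held as text, puts the case in June in tables whose purpose is to show month. A second text in the same annex points to exclusion, and the SAP does not choose between them.

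The inflation of June is 5% to 11% if 1% of onsets are year-only, 25% to 55% at 5%, and 50% to 110% at 10%. In each range the lower figure is for onsets even over May-October and the upper for onsets even over the year. The shares and both patterns are assumptions. If there are no year-only onsets, the effect is zero. Calendar-year tables do not change, because the year is known. An effect on season tables arises only if onset date assigns season.

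**What to change.** - In SAP 11.2.1, state that the 30 June rule is not used to assign month of onset, or season if onset date assigns season, and that this takes precedence over 11.2.2. Keep day 15 for a missing day.
- Add a month-unknown row, frequency only, to Templates 5-10 for year-only onsets. Keep these cases in the calendar-year tables.
- Count wholly missing onset dates separately.
- Report the number of partial and missing onset dates by country and, where the year is known, by year.

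The cost is one or two sentences, one row in six mock tables and one count. The dated month rows may then not sum to the yearly total; the month-unknown row and the count of missing dates account for the difference. If onset date assigns season, year-only cases leave the season tables, and the count shows how many.
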